4.2 Study rationale

Current FDA-approved treatment options for field-directed treatment of AK on the face and scalp are formulations containing diclofenac/hyaluronic acid (3 %/2.5 %), imiquimod cream (3.75%) or 5-fluorouracil, which require repeated applications for up to several months or lead to side effects related to erosive and/or inflammatory reactions induced by the treatment that may last for the entire treatment period or even longer (18–20).

Compared to methods like surgery, abrasion, cryosurgery, and alternative topical treatments, the use of PDT is advantageous for the field-directed treatment especially due to the high selectivity of treatment, but also to the short treatment period that is entirely controlled by the physician, and the excellent cosmetic results (21).

In addition, a European network meta-analysis of the relative clinical efficacy of 10 different treatment modalities for mild to moderate AK on the face and scalp, including PDT products as well as formulations containing cryosurgery, 5-fluorouracil, imiquimod, ingenol mebutate or diclofenac/ hyaluronic acid, has shown that ALA PDT using BF-200 ALA was the most efficacious treatment option (22).

Besides Ameluz[®], only one PDT product containing ALA is available in the US market. Levulan[®] Kerastick[®] providing ALA at a concentration of 20 % in a 2-component system that requires ALA to be compounded immediately before use. By label, the use of Levulan[®] Kerastick[®] is restricted to lesion-directed treatment of minimally to moderately thick AKs located on the face and scalp or the upper extremities. Ameluz[®] is the only PDT product available in the US market which has been approved for the field-directed treatment of AKs, but at the current time its label is restricted to the application of one tube of Ameluz[®].

In contrast to the currently marketed BF-RhodoLED[®] lamp the BF-RhodoLED[®] XL enables the illumination of a larger skin area in one step. The BF-RhodoLED[®] XL has 5 LED panels which are positioned in a curved shape.

This safety study is designed to confirm the safety and tolerability of BF-200 ALA (Ameluz[®]) in combination with BF-RhodoLED[®] XL for the field-directed treatment of mild to severe AK located on the face and scalp in an expanded treatment field of 60 cm², applying the content of 3 tubes of BF-200 ALA for PDT. Using the curved shape configuration of BF-RhodoLED XL permits an even illumination of the entire face or scalp and facilitates the illumination of discontinuous treatment field in one step.

4.3 Risk/benefit analysis

This safety study will include diseased subjects presenting with at least 8 mild to moderate AK lesions (≥ 4 mm) within the treatment field of about 60 cm² in total. In addition, severe AK lesions may be present in the treatment field. Subjects will receive BF-200 ALA treatment - already marketed for the treatment of AK in the US, EU, and Switzerland under the brand name Ameluz[®] - with conventional red-light illumination.

Clinical efficacy and safety of BF-200 ALA in combination with conventional red-light illumination for the treatment of mild to moderate AK on the face and scalp were previously examined in one dose-finding study, and three confirmatory studies encompassing a total of 885 randomized subjects comprising 462 subjects (2674 lesions) exposed to BF-200 ALA (7.8% ALA) (23–25) treated on the face and scalp. All subjects received up to 1 tube (2 g) of BF-200 ALA. In these pivotal clinical trials, complete response of subjects 12 weeks after the last PDT with BF-200 ALA was shown to be up to 90.9 % and total lesion response was up to 94.3 % (23–26).

In previous clinical trials with BF-200 ALA, local application site reactions were observed in 84-100 % of the subjects. These reactions are expected, given the therapeutic principle of PDT, which is based on phototoxic effects. The most common signs and symptoms were application site erythema, pain/burning, irritation, and edema. Most adverse reactions occurred during illumination or shortly afterwards. Symptoms were usually of mild or moderate intensity (investigator's assessment on a 4-point scale). Subjects treated with a higher dose (6 g / 3 tubes BF-200 ALA) within an enlarged treatment field of 60 cm² experienced more severe application site reactions (mainly pain, erythema) when treated on the face and scalp which was not reported for subjects treated in the periphery. Given that PDT pain was already described to be related to the size of treatment field (27), a higher pain intensity during treatment of an expanded treatment field on the face and/or scalp was to be expected. Nonetheless, application site pain during PDT is transient and well manageable. In most cases the symptoms lasted for 1 to 4 days, however, in some cases, they persisted for 1

to 2 weeks or even longer. It is known that the intensity of AEs depends on the applied light spectrum used for PDT and correlates with the higher response rate achieved by the use of narrow spectrum lamps, emitting around 630 nm, e.g. BF-RhodoLED®. In rare cases, adverse reactions may require interruption or discontinuation of the illumination.

Common adverse reactions of PDT with BF-200 ALA include headache and reactions at the application site, such as erythema, pain/burning, irritation (burning), edema, pruritus, exfoliation, scab, induration, vesicles. More detailed information on known adverse reactions is provided in the prescribing information (PI) for Ameluz® (28). This drug is contraindicated in subjects with known hypersensitivity to ALA, to porphyrins or to any excipients of Ameluz®, and in subjects with porphyria or photodermatoses.

It is assumed that local adverse reactions in the present study will be similar to those known from treatment of AK lesions as well as cancerous fields described previously. If required, pain management will be performed according to established guidelines (29,30) but restrictions for co-medications/treatments described in this protocol must be taken into consideration.

In this study, inclusion and exclusion criteria have been chosen to minimize possible risks due to the administration of BF-200 ALA, and to ensure a uniform study population. BF-200 ALA and the PDT lamp BF-RhodoLED® XL will be handled by appropriately trained study personnel. The setting of BF-RhodoLED® XL is comparable to BF-RhodoLED® used in the previous studies such that the emitted wavelength is 635 nm and same light dose of 37 J/cm² will be applied.

5 STUDY OBJECTIVES

5.1 Study objective

The objective of the study is to evaluate the safety and tolerability of BF-200 ALA PDT, utilizing BF-RhodoLED® XL illumination, in the treatment of mild to severe AK on the face and scalp in an expanded field-directed treatment.

The endpoints of the study are:

- Frequency and severity of adverse events (AEs), serious AEs (SAEs), and treatment-emergent adverse events (TEAEs). TEAEs are defined as all AEs with onset or worsening after treatment with IMP up to Visit 5
- Duration of TEAEs including the breakdown of severity category (mild, moderate, severe)
- Assessment of new lesions (AK, NMSC such as BCC, SCC or Bowens disease, and melanoma) if they occur inside the treatment field
- Assessment of new lesions (AK, NMSC, and melanoma) if they occur around the treatment field at a distance of < 10 cm
- Application site skin reactions during and post PDT, assessed by the investigator
- Application site discomfort during and post PDT, reported by the subjects
- Application site pain during illumination, as assessed by the subjects using an 11-point numeric rating scale
- Changes in vital signs
- Safety laboratory data
- Physical examination data
- Neurological assessments

6 STUDY DESIGN, DURATION AND DATES

[figure not shown]
6.1 Study design

This protocol describes a multicenter, open label study that will be conducted in the United States of America (US). Approximately 10 sites in the US will participate in this study. Each site should dose between 5 and 15 subjects. No site should dose more than 20 subjects unless prior approval of the sponsor is obtained. The maximum number should in no case exceed 25 subjects.

The clinical study will consist of:

- a screening visit (within 14 days before treatment), at which eligibility of subjects for study participation will be assessed (Visit 1)
- a baseline/treatment visit, at which eligible subjects will receive PDT with application of the content of 3 tubes of BF-200 ALA (Visit 2)
- two interim visits for safety assessment 7 days (\pm 2 days) (Visit 3) and 14 days (\pm 2 days) (Visit 4) post PDT
- a final clinic visit, 28 (\pm 7) days post PDT, at which safety and tolerability assessments will be performed (Visit 5)

[Figure 1](#) illustrates treatment details on study visits. An overview of scheduled assessments is provided in [Table 1](#).

* Visit 2 can be rescheduled once within 14 days after the scheduled date if the dosing day exclusion criterion (sunburn or other possible confounding skin conditions inside or in close proximity (< 10 cm distance) to the treatment field) is met and if the sunburn or other confounding skin conditions is/are expected to resolve within 14 days.

Figure 1: Summary of study visits

The PDT procedure (preparation of treatment field, drug application, incubation, illumination) will be performed similar to the prescribing information of Ameluz® (28). Details will be described in [Section 8](#).

6.2 Study duration, dates and end-of-study definition

For each subject the duration of the study is expected to be approx. 6 weeks. The overall study duration is estimated to be about 6.5 months (including an approx. 5-month recruitment phase). The duration of the overall study or the subject recruitment period may vary. The end of study will be defined as last subject last visit.

6.3 Definitions

Definition of treatment area:

For this study, the term treatment area defines the body region in which the treatment field is located. The following treatment areas will be investigated:

- **Face:** including forehead, excluding eyes, nostrils, and mouth
- **Scalp:** bald scalp, excluding ears

Definition of illumination area:

The “illumination area” is the area effectively illuminated by one BF-RhodoLED® XL lamp in one illumination session.

Definition of target lesions:

Target lesions are all AK lesions (mild to severe) located within the treatment field at Visit 1.

Definition of treatment field:

The “treatment field” is the part of the skin to which IMP is applied.

- The treatment field is defined as the skin surface area that is covered by IMP. In this study, the treatment field must comprise of a total skin area of approx. 60 cm² (~1 mm thick) and must contain at least 8 mild to moderate AK lesions with a diameter ≥ 4 mm. In addition, severe AK lesions might be present. AK target lesions included in the study should be entirely located within the treatment field, leaving a minimal distance of 1 cm of the lesion margin to the treatment field border. The treatment field has to be located on the face and/or the scalp (including forehead, excluding eyes, nostrils, ears, and mouth). The treatment field may be continuous or in several patches to form a total area of approximately 60 cm².
- In case of a discontinuous treatment field, all patches must be located within one effective illumination area.

Definition of new lesions

The term new lesion defines pre-neoplastic or neoplastic lesions including AK, NMSC such as BCC, SCC or Bowens disease, and melanoma that occur inside or in close proximity (< 10 cm distance) to the treatment field.

7 SELECTION OF SUBJECTS

7.1 Number of subjects

No sample size for the study was calculated. However, in agreement with FDA about 100 subjects are considered sufficient to evaluate the safety profile after application of the content of 3 tubes of BF-200 ALA. All subjects will receive BF-200 ALA.

7.2 Recruitment arrangements

Subjects will be screened at the study sites and if eligible, included into the study and subjected to PDT. Each site should dose between 5 and 15 subjects. A study site has to stop recruitment once 20 subjects have been treated unless prior sponsor approval is obtained. The maximum number should not exceed 25 subjects. Recruitment will be competitive within the limits described above.

7.3 Inclusion criteria

Eligible subjects must meet the following criteria:

1. Willingness and ability of subjects to provide informed consent and sign the Health Insurance Portability and Accountability Act (HIPAA) form. A study-specific informed consent and HIPAA form must be obtained in writing prior to starting any study procedures.
2. Subjects with mild to severe clinically confirmed AK lesions (according to Olsen (Olsen et al., 1991)) on the face and/or scalp. In case of severe AK lesions, a biopsy must be taken for confirmation of diagnosis. At least 8 mild to moderate AK lesions with a diameter of ≥ 4 mm must be present in the treatment field. The treatment field (continuous or in several patches) totaling about 60 cm^2 must be located within one effective illumination area. The AK lesions should be clearly distinguishable, without restrictions on the distance between lesions. Lesions should have a minimal distance of 1 cm between the lesion margin and the border of the treatment field.
3. All sexes, ≥ 18 years of age.
4. Willingness and ability to comply with study procedures, particularly willingness to receive a PDT session and to undergo 2 mm punch biopsy/biopsies in case of severe AK lesion(s) at the screening visit.
5. Subjects with good general health or with clinically stable medical conditions will be permitted to be included in the study. Subjects with clinically stable medical conditions will be permitted for inclusion into the study if not using prohibited medication.
6. Willingness to stop the use of moisturizers and any other non-medical topical treatments within the treatment field at least 24 h prior to the visits.
7. Acceptance to abstain from extensive sunbathing and the use of a solarium or tanning beds during the study.
8. For female subjects with reproductive potential: Negative serum pregnancy test.
9. For female subjects with reproductive potential: Effective contraception at screening visit and throughout the study.

7.4 Exclusion criteria

To reduce risks for the subjects and to ensure that the subjects are in a comparable status, subjects will be excluded if they meet at least one of the following exclusion criteria:

1. Any known history of hypersensitivity to ALA, porphyrins or excipients of BF-200 ALA.
2. History of soy or peanut allergy.
3. Subjects with sunburn or other possible confounding skin conditions (e.g. wounds, irritations, bleeding or skin infections) inside or in close proximity (< 10 cm distance) to the treatment field.
4. Clinically significant (CS) medical conditions making implementation of the protocol or interpretation of the study results difficult or impairing subject's safety such as:
 - a. Presence of photodermatoses or porphyria
 - b. Metastatic tumor or tumor with high probability of metastasis
 - c. Infiltrating skin neoplasia (suspected or known)
 - d. Unstable cardiovascular disease (New York Heart Association class III, IV)
 - e. Unstable hematologic (including myelodysplastic syndrome), hepatic, renal, neurologic, or endocrine condition
 - f. Unstable collagen-vascular condition
 - g. Unstable gastrointestinal condition
 - h. Immunosuppressive condition
 - i. Presence of clinically significant inherited or acquired coagulation defect
5. Clinical diagnosis of atopic dermatitis, Bowen's disease, basal cell carcinoma, eczema, psoriasis, rosacea, squamous cell carcinoma, other malignant or benign tumors inside or in close proximity (< 10 cm distance) to the treatment field.
6. Presence of strong artificial pigmentation (e.g. tattoos) or any other abnormality that may impact lesion assessment or light penetration in the treatment field.
7. Any physical therapy such as cryosurgery, laser therapy, electrodessication, microdermabrasion, surgical removal of lesions, curettage, or treatment with chemical peels such as trichloroacetic acid inside or in close proximity (< 10 cm distance) to the treatment field within 4 weeks prior to screening.
8. Any of the topical treatments defined below within the designated periods prior to screening:
 - a. Topical treatment with ALA or ALA esters (e.g. methyl aminolevulinic acid (MAL)) or an investigational drug in- and outside the treatment field within 8 weeks.
 - b. Topical treatment with immunosuppressive, cytostatic or cytotoxic drugs inside or in close proximity (< 10 cm distance) to the treatment field within 8 weeks.
 - c. Start of topical administration of a medication with hypericin or other drugs with phototoxic or photoallergic potential inside or in close proximity (< 10 cm distance) to the treatment field within 4 weeks. Subjects may, however, be

eligible if such medication was applied for more than 4 weeks prior to screening without evidence of an actual phototoxic/photoallergic reaction.

9. Any use of the systemic treatments within the designated periods prior to screening:
 - a. Cytostatic or cytotoxic drugs within 6 months.
 - b. Immunosuppressive therapies or use of ALA or ALA esters (e.g. MAL) within 12 weeks.
 - c. Drugs known to have major organ toxicity within 8 weeks or an investigational drug.
 - d. Interferon or glucocorticosteroids within 6 weeks.
 - e. Start of intake of medication with hypericin or systemically acting drugs with phototoxic or photoallergic potential within 8 weeks prior to screening.
Subjects may, however, be eligible if such medication was taken in for more than 8 weeks prior to the screening visit without evidence of an actual phototoxic/photoallergic reaction.
10. Breast feeding women.
11. Suspicion of drug or alcohol abuse.
12. Subjects unlikely to comply with protocol, e.g. inability to return for visits, unlikely to complete the study, or inappropriate in the opinion of the investigator.
13. A member of study site staff or sponsor staff directly involved in the conduct of the protocol or a close relative thereof.
14. Simultaneous participation in another clinical study.

Re-screening of subjects is allowed once in case exclusion criterion 3 is met and eligibility can be achieved within 14 days.

Dosing day exclusion criteria:

At Visit 2 (baseline, PDT-1)

Subjects with sunburn or other possibly confounding skin conditions (e.g. wounds, irritations, bleeding or skin infections) inside or in close proximity (< 10 cm distance) to the treatment field. Re-assessment of subjects is allowed within 14 days once the sunburn or other confounding skin conditions is/are expected to resolve.

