7. Any physical therapy such as cryosurgery, laser therapy, electrodesiccation, microdermabrasion, surgical removal of lesions, curettage, or treatment with chemical peels such as trichloroacetic acid inside or in close proximity (< 10 cm distance) to the treatment field within 4 weeks prior to screening.
8. Any of the topical treatments defined below within the designated periods prior to screening:
 - a. Topical treatment with ALA or ALA esters (e.g. methyl aminolevulinic acid (MAL)) or an investigational drug in- and outside the treatment field within 8 weeks.

- b. Topical treatment with immunosuppressive, cytostatic or cytotoxic drugs inside or in close proximity (< 10 cm distance) to the treatment field within 8 weeks.
- c. Start of topical administration of a medication with hypericin or other drugs with phototoxic or photoallergic potential inside or in close proximity (< 10 cm distance) to the treatment field within 4 weeks. Subjects may, however, be eligible if such medication was applied for more than 4 weeks prior to screening without evidence of an actual phototoxic/photoallergic reaction.

9. Any use of the systemic treatments within the designated periods prior to screening:

- a. Cytostatic or cytotoxic drugs within 6 months.
- b. Immunosuppressive therapies or use of ALA or ALA esters (e.g. MAL) within 12 weeks.
- c. Drugs known to have major organ toxicity within 8 weeks or an investigational drug.
- d. Interferon or glucocorticosteroids within 6 weeks.
- e. Start of intake of medication with hypericin or systemically acting drugs with phototoxic or photoallergic potential within 8 weeks prior to screening. Subjects may, however, be eligible if such medication was taken in for more than 8 weeks prior to the screening visit without evidence of an actual phototoxic/photoallergic reaction.

10. Breast feeding women.

11. Suspicion of drug or alcohol abuse.

12. Subjects unlikely to comply with protocol, e.g. inability to return for visits, unlikely to complete the study, or inappropriate in the opinion of the investigator.

13. A member of study site staff or sponsor staff directly involved in the conduct of the protocol or a close relative thereof.

14. Simultaneous participation in another clinical study.

Re-screening of subjects is allowed once in case exclusion criterion 3 is met and eligibility can be achieved within 14 days.

Dosing day exclusion criteria

At Visit 2 (baseline, PDT-1)

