- Any therapy such as cryosurgery, laser therapy, electrodesiccation, surgical removal of lesions, curettage, or treatment with chemical peels such as trichloroacetic acid inside or in close proximity (< 10 cm distance) to the treatment field 4 weeks prior to screening until end-of-study. Lesions may be treated with these methods if the distance to the treatment field is more than 10 cm.
- A list of forbidden, concomitant medication is provided in [Table 4](#).

If the investigator, at any time in the study, suspects a lesion inside or outside the treatment field to have progressed into a manifest malignancy, they should refer the subject for standard medical treatment, irrespective of whether or not this results in exclusion of the subject from the study.

Table 4: List of forbidden concomitant medication with designated time periods.

Medication	Topical administration		Systemic administration	
	start of restriction	forbidden until	start of restriction	forbidden until
ALA or ALA-esters (except IMP at Visit 2)	8 weeks prior to Visit 1	end-of-study	12 weeks prior to Visit 1	end-of-study

Medication	Topical administration		Systemic administration	
	start of restriction	forbidden until	start of restriction	forbidden until
Cytotoxic drugs/ Cytostatic drugs	8 weeks prior to Visit 1 inside or in close proximity (< 10 cm distance) to the treatment field	end-of-study inside or in close proximity (< 10 cm distance) to the treatment field	6 months prior to Visit 1	end-of-study
Immunosuppressive therapies	8 weeks prior to Visit 1 inside or in close proximity (< 10 cm distance) to the treatment field	end-of-study inside or in close proximity (< 10 cm distance) to the treatment field	12 weeks prior to Visit 1	end-of-study
	7 days prior to PDT inside and outside the treatment field	7 days post PDT inside and outside the treatment field		
Interferon	---	---	6 weeks prior to Visit 1	end-of-study
Glucocorticosteroids	(allowed)	(allowed)	6 weeks prior to Visit 1 ^a	end-of-study ^a
NSAIDs (others than listed below)	7 days prior to PDT	7 days post PDT	7 days prior to PDT	7 days post PDT
Acetylsalicylic acid > 3750 mg/day	---	---	7 days prior to PDT	7 days post PDT
Ibuprofen > 1200 mg/day	---	---	7 days prior to PDT	7 days post PDT
Diclofenac	7 days prior to PDT within illumination area(s) ^b	7 days post to PDT within illumination area(s) ^b	> 100 mg/day; 7 days prior to PDT	> 100 mg/day; 7 days post PDT

Medication	Topical administration		Systemic administration	

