	start of restriction	forbidden until	start of restriction	forbidden until
Hypericin or drugs with phototoxic/ photoallergic potential^c	4 weeks prior to Visit 1 inside or in close proximity (< 10 cm distance) to the treatment field	end-of-study inside or in close proximity (< 10 cm distance) to the treatment field	8 weeks prior to Visit 1	end-of-study
Investigational drugs	8 weeks prior to Visit 1	end-of-study	8 weeks prior to Visit 1	end-of-study
Drugs known to have major organ toxicity	---	---	8 weeks prior to Visit 1	end-of-study
Medication that influence coagulation (e.g. anticoagulants, anti-platelet drugs)	---	---	Visit 1 (may be used throughout the study if taken in a stable dose prior to study)	end-of-study (may be used throughout the study if taken in a stable dose prior to study)
EMLA® cream	On day of PDT inside or in close proximity (< 10 cm distance) to the treatment field	On day of PDT inside or in close proximity (< 10 cm distance) to the treatment field	---	---

^a Not for inhaled glucocorticosteroids.

^b Topical use of diclofenac up to 2.5 % may be used outside illumination area(s) throughout the study.

^c Start of therapy with any photosensitizer or systemically-acting drugs with phototoxic or photoallergic potential, such as psoralenes, tetracyclines, nalidixic acid, furosemide, amiodarone, phenothiacines, chinolones, fibrates, or phytotherapy with St. John's wort, arnica, or valerian or topically applied phototoxic substances like tar, pitch, psoralenes or some dyes like thiazide, methylene blue, toluidine blue, eosin, rose bengal, or acridine within 4 weeks for topical administration or 8 weeks for systemic administration prior to screening. Subjects may, however, be eligible if such medication was taken longer than 4 weeks (topical) or 8 weeks (systemic) prior to screening without evidence of an actual phototoxic/photoallergic reaction.

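### Exclusion 8c and the matching Table 4 row restrict newly started topical phototoxic drugs by distance from the gel alone, so an off-centre field under a large lit area can leave lit skin uncovered; a low-weight precaution.

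*Protocol*

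**What the plan says.** **The rule.** Protocol 7.4, exclusion 8c, covers hypericin and "other drugs with phototoxic or photoallergic potential inside or in close proximity (< 10 cm distance) to the treatment field within 4 weeks" before screening. The synopsis (section 2) repeats it: "Start of topical administration of a medication with hypericin or other drugs with phototoxic or photoallergic potential inside or in close proximity". Subjects who have used the product for more than 4 weeks remain eligible if this was "without evidence of an actual phototoxic/photoallergic reaction".

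**Table 4 (Protocol 9.2).** The topical cells of the hypericin/phototoxic row read "4 weeks prior to Visit 1 inside or in close proximity (< 10 cm distance) to the treatment field" for the start and "end-of-study inside or in close proximity (< 10 cm distance) to the treatment field" for the end. Footnote c gives examples (tar, psoralenes, several dyes) and repeats the window, "within 4 weeks for topical administration or 8 weeks for systemic administration prior to screening", without a distance.

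**Gel and light are separate zones.** Protocol 6.3 defines the treatment field by where gel is applied (about 60 cm²) and the illumination area by what one XL lamp lights in a session. Section 8.1.2 gives that area a maximum of 23 x 29 cm, and section 4.2 presents the lamp as able to light a whole face or scalp. The field must lie inside one illumination area; no rule centres it. Section 8.4 requires goggles and describes no shielding of gel-free skin, but refers to a user manual for further precautions.

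**Neighbouring rules use other zones.** Topical ALA, its esters "or an investigational drug in- and outside the treatment field within 8 weeks" are barred under 8a. Newly started systemic phototoxic drugs (9e) have no distance limit. Topical diclofenac is limited by the lit zone ("7 days prior to PDT within illumination area(s"). The SAP sets no zone of its own.

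**The concern.** The exemption in 8c turns on whether a phototoxic or photoallergic reaction has occurred, so the rule is aimed at reactions that need light. Its zone, however, is measured from the gel. A subject could have started a tar, psoralene or dye product in the last 4 weeks on facial or scalp skin more than 10 cm from the gel, have that skin lit for 10 minutes, and not meet 8c. The Table 4 cells run to the end of the study, so they leave the same gap for a product started between Visit 1 and PDT. Footnote c, with no distance, lets sites read the row two ways.

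What is at stake is the completeness of a risk-reduction rule in a study of a lamp not yet approved in the US. No endpoint or analysis depends on it.

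**Working it through.** **Inputs from the Protocol.** Maximum illumination area 23 x 29 cm (8.1.2); field about 60 cm² (6.3); restricted zone inside or less than 10 cm from the field (7.4, Table 4).

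**The plan's own figure.** 23 x 29 = 667 cm², as stated in 8.1.2.

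**Assumptions, not in the documents.** Lit skin is a flat oval inscribed in the stated rectangle, of area π x 11.5 x 14.5 = 523.9 cm². The field is a circle of radius √(60/π) = 4.37 cm, a square of side √60 = 7.75 cm, a 15 x 4 cm band, or split patches totalling 60 cm².

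**Measure.** Share = (lit area at least 10 cm from the nearest field border) / (lit area), on a 0.02 cm grid.

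| Field in the 23 x 29 cm oval | Share | Area |
|---|---|---|
| Circle, centred | 0.2% | 0.9 cm² |
| Square, centred | 1.1% | 5.5 cm² |
| Circle or square, 3 cm off-centre | 2% to 9% | 11 to 45 cm² |
| Circle or square, at the edge | 23% to 39% | 122 to 204 cm² |
| 15 x 4 cm band across the short axis, centred | 8% | 44 cm² |
| Same band, 8 cm toward one end | 33% | 173 cm² |
| Two 30 cm² patches side by side on the short axis | 5% | 28 cm² |
| Two patches along the long axis, or three or four spread patches | 0% | 0 cm² |

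**Smaller assumed ovals, circular field.**

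| Oval | Centred | 3 cm off-centre | Edge, short axis | Edge, long axis |
|---|---|---|---|---|
| 20 x 25 cm | 0% | 0% (short axis) to 2% (long axis) | 8% | 25% |
| 15 x 20 cm | 0% | 0% | 0% | 3% |
| 14 x 18 cm | 0% | 0% | 0% | 0% |

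**Hand check.** For a circle touching one end of an axis, the opposite end lies (axis length − 2 x 4.37) cm from the field border:
- 29 cm axis: 29 − 8.74 = 20.26 cm, well beyond 10.
- 20 cm axis: 20 − 8.74 = 11.26 cm, just beyond 10.
- 18 cm axis: 18 − 8.74 = 9.26 cm, inside the restricted zone, hence 0%.
- 15 cm axis: 15 − 8.74 = 6.26 cm, also 0%.

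**Rectangle instead of oval.** If skin filled the full rectangle, a centred square would leave 9% and a centred circle 13%. Most of that lies in the corners, which a face or scalp is unlikely to fill, so the oval is the fairer basis.

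**The case against.** The case against changing anything is substantial.

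- **No hazard is shown.** Nothing in the documents says that the listed products react to red light near 635 nm. This stands, and it limits the point to a precaution.
- **Edge placement is a worst case.** Section 8.1.2 has the panels adjusted to the treatment field under a low-intensity light, 23 x 29 cm is a maximum, and section 8.4 records which panels were used, so fewer than five may be lit. This stands; the larger percentages are upper-end cases. Adjustment to the field is still not a centring rule.
- **Shielding may be described elsewhere.** The user manual is not available here. One can say only that the Protocol describes none.
- **Partial safeguards exist.** Criterion 12 lets the investigator exclude a subject judged inappropriate, and section 9.2 asks subjects to confer before using new medication. Both help, but neither is tied to lit skin. Footnote c could be read as having no distance limit, but it annotates cells that carry one.
- **Ten centimetres is the Protocol's usual buffer, and diclofenac is an NSAID.** True. The diclofenac row shows only that sites are already given a lit-skin zone, not that it was chosen for phototoxicity.
- **The illumination area and the lamp are known for certain only at Visit 2.** This stands and shapes the fix.

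A reader might go further and infer that the gap exposes subjects to a known phototoxic risk, that other ALA products are allowed on lit skin, or that reactions there would confuse the safety results. The documents support none of these. No such risk is documented. Criterion 8a and Table 4 bar topical ALA and its esters at any site. Sections 10.2.7 and 11.3 keep application site reactions, which occur in the treatment field, apart from other AEs.

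**Conclusion.** The point holds as a wording gap of low weight. The rule addresses reactions that need light but stops 10 cm from the gel, so it misses lit skin when the field is off-centre and the lit area is large. For compact centred fields or well-spread patches the gap is negligible. It becomes material only toward the edge of an area near the lamp's maximum and disappears in a 14 x 18 cm oval.

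These sizes rest on flat ovals and simple field shapes; the documents give neither actual lit areas nor field positions. An affected subject would also need a recently started topical photosensitiser on that particular skin. How many of the roughly 100 subjects would qualify cannot be estimated, and the number may be zero.

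**What to change.** Keep the 10 cm zone and the exemption for more than 4 weeks of use without a reaction. Add *or within the planned illumination area* to exclusion 8c, its synopsis copy, and both topical cells of the hypericin/phototoxic row in Table 4. On lit skin, the cells and footnote c would then agree.

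Sites would judge the planned area at screening, when the field is selected, and confirm it at the existing Visit 2 eligibility re-check for the lamp actually used. The second step is needed because 6.3 defines the illumination area for the XL lamp only, while 8.1.2 allows the standard BF-RhodoLED if the XL fails. Inclusion criterion 2 and the diclofenac cell already make sites consider the illumination area before PDT, although they are not asked to map its border.

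The cost is one phrase in four places, possibly a few more exclusions or late screen failures, and, if the study has started, an amendment that needs approval before use if classed as substantial (Protocol 15.6 and 15.7). No visit, procedure, eCRF item or analysis is added.
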